NCT #: 05313009

MUSC CTO #: 103408

A PHASE 1B TRIAL OF TARLOXOTINIB AND SOTORASIB IN PATIENTS WITH KRAS G12C MUTATIONS

PRINCIPAL INVESTIGATOR:

[name] PhD
Medical University of South Carolina
[name]
[name]
[contact]
[contact]
E-mail: [contact]

STATISTICIAN:

[name].
Medical University of South Carolina
[name]
[name]
[contact]
[contact]
E-mail: [contact]

CO-INVESTIGATOR:

[name] MPH
Medical University of South Carolina
[name]
[name]
[contact]
[contact]
E-mail: [contact]

COORDINATING OFFICE:

Sponsor-Investigator Support Unit

Hollings Cancer Center Clinical Trials Office
[name]
[name]
[contact]
[contact]

PROTOCOL VERSION HISTORY

Version 1 dated August 17, 2021

Version 2 dated October 6, 2021

Version 3 dated February 27, 2023

SYNOPSIS

Study Number	103408
Sponsor	Rain Therapeutics
Phase	Phase IB
Objectives	
Primary Objectives
 
 - To evaluate the RP2D, safety, and tolerability of tarloxotinib in combination with sotorasib in patients with KRAS G12C mutated advanced non-small cell lung cancer (NSCLC) -To evaluate the tumor objective response rate (ORR) assessed by RECIST 1.1 criteria of the combination of tarloxotinib with sotorasib 
Secondary Objectives
 
To evaluate other measures of efficacy of the combination of tarloxotinib with sotorasib in patient with KRAS G12C mutated advanced NSCLC

Study Design	This is a Phase IB dose expansion trial with safety lead-in evaluating the safety, clinical activity/efficacy of the combination of tarloxotinib and sotorasib in patients with KRAS G12C mutation who have progressed on any small molecule targeting KRAS G12C mutant Non-Small Cell lung cancer.
Treatment	
Sotorasib 960 mg PO daily + tarloxotinib IV weekly at the combination RP2D determined in the safety lead-in
 
Treatment cycle: Day 1, 8, 15, 22 of every 28-day cycle
 
Tumor assessment every 8 weeks

Eligibility	
Inclusion
 
 1) Histologically confirmed diagnosis of squamous or non-squamous NSCLC with KRAS G12C mutation 2) Unresectable or metastatic disease 3) No available treatment with curative intent 4) Must have previously received treatment with a platinum-containing chemotherapy regimen. Additional prior therapies for metastatic KRAS G12C mutated NSCLC are also permitted. 5) Must have previously received at least one month trial of sotorasib or a therapy targeting KRAS G12C mutation with documented progression. If sotorasib dose from prior therapy was reduced for toxicity, patients that meet the above criteria are expected to receive study treatment at the reduced dose. 6) Must have measurable or evaluable disease as defined by RECIST 1.1 7) Age >18 years 8) Life expectancy of at least 3 months 9) Recovery from adverse effect of prior therapy at the time of enrollment 10) Eastern Cooperative Oncology Group (ECOG) performance status of 0 or 1 11) Laboratory values within the screening period: 
 a) Absolute neutrophile count > 1000/mm³ b) Platelet count > 100,000 /mm³ c) Hemoglobin > 8 in the absence of transfusions for at least 2 weeks d) Total bilirubin < 1.5 x upper limit of normal (or < 3 x ULN if associated with liver metastases or Gilbert's disease) e) Aspartate transaminase (AST) or alanine transaminase (ALT) < 3 x ULN (or < 5x ULN if associated with liver metastases) f) Creatinine clearance (CrCl) > 60 mL/min calculated by CKD-EPI or MDRD 12) Women of child-bearing potential agrees to use contraception while participating in the study and for a period of 6 months following termination of study treatment 13) Completed informed consent process

	
14) Willing to comply with clinical trial instructions and requirements.
 
Exclusion
 
1) Active, untreated brain metastases. Patients are eligible if brain metastases are previously treated and asymptomatic. Patients must be neurologically stable and on a stable or tapering dose of corticosteroids for at least 2 weeks prior to C1D1.
 
2) History of intestinal disease or major gastric surgery likely to alter absorption of study treatment or inability to swallow pills
 
3) Congestive heart failure > NYHA Class 3
 
4) QTc > 480 milliseconds or family history of Long QT syndrome
 
5) Ongoing need for a medication with a known risk of Torsades de Pointes that cannot be switched to alternative treatment prior to study entry.
 
6) Pregnancy or breast feeding
 
7) Has other known non-KRAS G12C activating oncogene-driver mutations, including but not limited to: ALK, ROS1, RET, BRAF, NTRK1/2/3, MET, EGFR
 
8) Previously have received anti-EGFR or anti-HER2 TKIs
 
9) Previously have received anti-EGFR or anti-HER2 monoclonal antibodies
 
10) Clinically active or symptomatic interstitial lung disease
 
11) Known concurrently malignancy that is expected to require active treatment within 2 years or may interfere with the interpretation of the efficacy and safety outcomes of this study.
 
12) Infection requiring systemic treatment within 7 days prior to cycle 1 day1.
 
13) Patients with known hypersensitivity to either tarloxitinib, sotorasib, or any of the ingredients.

Criteria for Efficacy Evaluation	Objective response (OR = CR+PR) measured by CT and assessed per RECIST 1.1. Complete response (CR) and Partial response (PR) require confirmatory CT repeat assessment at least 4 weeks after the first detection of response
Criteria for Safety Evaluation	Dose-limiting toxicities, treatment-emergent adverse events, treatment-related adverse events, clinically significant changes in vital signs, electrocardiograms, laboratory tests
Statistical Methods	
Analysis Populations
 
The following analysis sets will be defined for this study.
 
The safety analysis set comprises all enrolled patients who receive any quantity of study treatment, regardless of eligibility. The safety evaluation will be performed based on the first dose of study treatment a patient receives, regardless of the patient's cohort assignment. The safety analysis set will be used for all dosing/exposure and safety analyses.

[figure not shown]
	
The DLT-evaluable population (safety lead-in only) comprises patients who have either completed the DLT-observation period (1 cycle, 28 days) and received at least 75% of planned doses of the tarloxotinib and sotorasib combination in cycle 1 or have discontinued study treatment or study participation before completing cycle 1 due to a DLT.
 
The intention to treat (ITT) analysis set comprises all patients in the safety analysis set eligible for study inclusion and who meet the inclusion criteria for dose expansion, including eligible safety lead-in patients treated at the combination RP2D. This analysis set will be used for all efficacy analyses.
 
Safety lead-in
 
A minimum of 6 patients and as many as 18 patients will be enrolled in a safety lead-in cohort to evaluate the safety of the combination of tarloxotinib and sotorasib. Sotorasib will be held at a fixed dose of 960 mg QD (the approved dose) while the starting dose of tarloxotinib will be the monotherapy RP2D equal to 150mg/m² QW (dose level 1 [DL1]). Following a 3+3 algorithm, an initial 3 patients will be enrolled at DL1. If 0 or 1 of 3 patients experience a DLT, an additional 3 patients will be enrolled to DL1. DL1 will be declared the combination RP2D (RP2D_c) if at most 1 of 6 patients treated at DL1 experience a DLT. Alternatively, if there are 2 or more DLTs observed at DL1, 3 patients will be enrolled at DL -1 and the 3+3 rules repeated for safety evaluation. The RP2D_c will be the highest DL at which at most 1 patient of 6 experiences a DLT. If DL -2 is considered too toxic, additional dose levels below DL -2 may be evaluated for safety.
 
Dose expansion
 
Once the tarloxotinib RP2D_c is reached, an expansion cohort of up to 12 patients will be enrolled to evaluate the safety of the combination of tarloxotinib and sotorasib. Eligible safety lead-in patients treated at the RP2D_c will be included in the expansion cohort.

--	---

TABLE OF CONTENTS

1	SCHEMA	6

1 SCHEMA

This is a Phase IB dose expansion trial with safety lead-in evaluating the safety, clinical activity/efficacy of the combination of tarloxotinib and sotorasib in patients with KRAS G12C mutation who have progressed on any small molecule targeting *KRAS G12C* mutant Non-Small Cell lung cancer.

3+3 design to de-escalate tarloxotinib dosing based on DLTs

Dose level	Sotorasib	Tarloxitinib
-2	960 mg PO daily	75 mg/m ² IV weekly
-1	960 mg PO daily	100 mg/m ² IV weekly
0 (full dose)	960 mg PO daily	150 mg/m ² IV weekly

2 OBJECTIVES AND ENDPOINTS

2.1 PRIMARY OBJECTIVE

Objectives	Endpoints
To evaluate the RP2D, safety, and tolerability of tarloxotinib in combination with sotorasib in patients with KRAS G12C mutated advanced non-small cell lung cancer (NSCLC).	Dose-limiting toxicities, treatment-emergent adverse events, treatment-related adverse events, clinically significant changes in vital signs, electrocardiograms, laboratory tests
To evaluate the tumor objective response rate (ORR) assessed by RECIST 1.1 criteria of the combination of tarloxotinib with sotorasib	Objective response (OR = CR+PR) measured by CT and assessed per RECIST 1.1. Complete response (CR) and Partial response (PR) require confirmatory CT repeat assessment at least 4 weeks after the first detection of response

2.2 SECONDARY OBJECTIVES

Objectives	Endpoints
To evaluate other measures of efficacy of the combination of tarloxotinib with sotorasib in patient with KRAS G12C mutated advanced NSCLC	
 - Duration of response (DOR) as measured from the date of first response to date of disease progression or death - Disease control rate (DCR) based on patient who had CR or PR or Stable disease (SD) for at least 2 cycles (8 weeks) - Best overall response (BOR) - Progression free survival (PFS) as measured from the date of first study drug dose to the date of the first objective documentation of radiographic disease progression or death due to any cause - Overall survival (OS) as measured from the date of first study drug dose to the date of death by any cause

3 BACKGROUND

3.1 STUDY RATIONALE

3.1.1 Introduction

KRAS acts as a key protein in transducing signals from cell surface receptors, such as receptor tyrosine kinases (RTKs) into cells to initiate a network of cytoplasmic and nuclear signaling cascades that mediate key processes, such as cell cycle entry and cell survival that regulate

normal tissue homeostasis(1). Due to the central importance of KRAS in mediating critical cellular processes, there are significant interconnected signaling feedback pathways that protect normal cells from uncontrolled proliferation and cell death. These signaling feedback pathways are also activated by tumor cells upon inhibition of mutated *KRAS*, which may result in intrinsic or acquired resistance to small molecule *KRAS G12C* inhibitors. Pre-clinical studies in non-small cell lung cancer (NSCLC) have shown that a key pathway that may be activated upon KRAS inhibition is the upstream ERBB RTKs, which provides the rationale for dual *KRAS* and ERBB blockade in overcoming resistance mechanisms in *KRAS* mutated NSCLC(2).

3.1.2 Non-small cell lung cancer

Lung cancer is the second most common cancer and the leading cause of cancer death in the United States. There were approximately 247,270 new cases of lung cancer that occurred in 2020 (3). Prior studies have reported that lung cancer resulted in more deaths than breast cancer, prostate cancer, colorectal cancer, and leukemia combined in men ≥ 40 years old and women ≥ 60 years old. The past decade has seen a revolution of new advances in the management of non-small cell lung cancer (NSCLC) with remarkable progresses in screening, diagnosis, and treatment. The advances in systemic treatment have been driven primarily by the development of molecularly targeted therapeutics, immune-checkpoint inhibitors and anti-angiogenic agents, all of which have transformed this field with significantly improved patient outcomes. Despite these advances, most patients with advanced NSCLC have incurable disease, particularly after failure of a platinum-based chemotherapy regimen and check point inhibitors.

3.1.3 KRAS G12C mutated lung cancer

One of the earliest identified molecular drivers of NSCLC is the GTPase transductor protein called KRAS. It is a member of the RAS family of oncogenes and at the apex of multiple signaling pathways central to tumor cell proliferation. KRAS mutant lung cancers have worse outcomes in both early stage and advanced metastatic settings, illustrating the critical need for novel agents targeting KRAS-driven NSCLC. *KRAS G12C* mutations are present in ~15% of lung adenocarcinomas and 0-8% of other cancers(2). The missense mutation at codon 12 interferes with the GTPase, activating protein mediated GTP hydrolysis and shifting the equilibrium between the signaling-competent KRAS-GTP and signaling incompetent KRAS-GDP in favor of the GTP bound state. This process links upstream cell surface receptors such as the ERBB family (EGFR, HER-2, HER-3, HER-4) to downstream pathways such as RAF/MEK/ERK and PI3K/AKT/mTOR which leads to uncontrolled cell proliferation and survival.

Attempts to identify small molecular inhibitors of KRAS have been unsuccessful for many years as there was a lack of a clearly defined deep pocket in the structure of RAS outside of the nucleotide binding site and the challenge of targeting the nucleotide binding site due to extraordinarily high affinity of GTP. Recently, several pioneering studies have identified small molecule cysteine-reactive inhibitors that covalently modify the mutant KRAS G12C protein to reveal an allosteric switch II pocket(4, 5). The induction of the structurally disordered pocket by these small molecule inhibitors converts the GTP preference of naïve KRAS G12C to the inactive GDP bound state, impairing its interaction with downstream effectors.

AMG510/Sotorasib was the first KRAS G12C inhibitor to enter the clinic. A Phase I/II clinical trial involving 129 patients included 59 patients with *KRAS G12C* mutated NSCLC who had progressed on prior standard therapies. Patients were enrolled in dose escalation and expansion cohorts to receive daily sotorasib monotherapy (960 mg PO daily) (6). At a median follow up of 12.2 months, approximately 50% of NSCLC patients demonstrated tumor regression with a confirmed objective response rate (ORR) of 37.1% (95% CI 28.6-46.2%) and a disease control rate (DCR) of 80.6% (95% CI 72.6-87.2%). The median time to objective response was 1.4 months and median duration of response was 10 months, with median progression free survival (PFS) of 6.8 months. The FDA has now accepted a new drug application and granted it a priority review for the treatment of patients with *KRAS G12C* mutant locally advanced or metastatic NSCLC following at least 1 prior systemic treatment, with an expected decision date by August 2021.

Although the results from these early-stage clinical trials showed promise, ~50% of KRAS G12C mutant NSCLC patients failed to respond to therapy and rate of relapse is high calling for the need for novel combinations to overcome intrinsic and acquired resistance mechanisms in this subset of patients.

3.1.4 Rationale for the combination of KRAS G12C inhibitors with pan-ERBB inhibition

It was previously thought that constitutively active oncogenic KRAS induces growth factor independence. However, recent evidence has suggested that specific *KRAS* mutant isoforms such as *KRAS G12C* may be regulated by upstream activation of several receptor tyrosine kinases. Lito *et. al.* demonstrated that concurrent EGFR and G12C inhibition potentiated growth inhibition in two different *KRAS G12C* mutant NSCLC cell lines(7). The pattern of RTK dependence appears to vary between *KRAS G12C* mutant cancer but numerous RTKs are involved in the adaptive feedback mechanism to G12C inhibition. This may be mediated through an adaptive RAS pathway activation. Misale *et. al.*, identified several RTK inhibitors exhibiting strong synergies with G12C inhibitors(8). Umelo *et. al.* examined RTK dependent cell lines to provide evidence that in a group of mutant *KRAS G12C* NSCLC lines, HER2 and HER3 are major upstream signaling activators(9). They examined several NSCLC lines to show that EGF or NRG1 beta stimulation can strongly enhance the amount of active RAS in cells harboring oncogenic KRAS G12C, which suggest that some KRAS mutant cancers retain sensitivity to upstream stimuli emanating from extracellular signaling via the ERBB pathway. Silencing oncogenic KRAS in EGFR/HER dependent cells reduced cellular growth and induced a modest apoptotic signal. The depletion of KRAS expression by mutant specific siRNA was accompanied by a reduction in AKT phosphorylation in the ERBB dependent subset and activation of STAT3, which suggests a feedback loop via STAT3 that re-establishes oncogenic signaling thereby compensating for the loss of AKT survival signals. Pan ERBB inhibition in these *KRAS G12C* mutated NSCLC lines resulted in a potent suppression of growth and inhibition of receptor signaling and downstream signaling effectors. Thus, sole silencing of oncogenic KRAS may not be an effective therapeutic strategy in KRAS-addicted cancers since upstream events and feedback loops are likely to attenuate or annul the effects of the therapeutic intervention. These pre-clinical studies provide a solid ground to evaluate the use of pan-ERBB inhibitors in combination with *KRAS G12C* inhibitors in patients with KRAS mutant lung tumors.

3.1.5 Tarloxotinib

Tarloxotinib is a recently discovered novel prodrug that releases a potent, irreversible pan-ERBB (EGFR, HER2 and HER4) TKI. It is designed to be inactive under normal oxygen conditions but undergoes fragmentations under low oxygen conditions (hypoxia) to release the potent irreversible active metabolite (tarloxotinib-E) that has activity against both normal and mutant versions of the ERBB family(10). Selective production of tarloxotinib-E under hypoxic conditions generates a therapeutic window where it is selectively activated in hypoxic tumor regions to deliver higher drug delivery to tumor tissue. This reduces systemic exposure which avoids on-target EGFR related toxicities than standard EGFR TKI. In a mouse xenograft model of a human derived EGFR exon 20 insertion, intra-tumoral tarloxotinib-E levels were 20 time higher than skin and 50 times higher than plasma demonstrating selective tumor conversion. This strategy broadens the therapeutic window leading to improved efficacy, while reducing toxicity. Multiple pre-clinical studies have further demonstrated the efficacy of tarloxotinib compared to standard EGFR inhibitors(11).

Phase I clinical trials to determine the MTD and DLTs of tarloxotinib, enrolled 27 patients with locally advanced or metastatic solid tumors(12). Of the patients that received tarloxotinib as a weekly 1-hour infusion, 6 patients received the drug at the recommended Phase 2 dose of 150 mg/m² with good tolerance.

3.1.6 Combination of Sotorasib with Tarloxotinib

The combination of tarloxotinib with sotorasib is poised to provide highly specific tumor inhibition while targeting the vertical KRAS signaling pathway with minimal toxicity. The combination is unlikely to result in clinically relevant drug-drug interaction (DDI) based on absorption, metabolism, elimination or protein-binding. Tarloxotinib is intravenously administered while sotorasib is a small molecule that is administered orally; no absorption interactions are expected.

Table 2 provides a comparison of the toxicity noted in Phase I/II clinical trials of these two drugs. The safety profile is expected to be generally non-overlapping with the exception of gastrointestinal adverse events that include nausea and diarrhea.

3.1.7 Comparison of Toxicity reported in the individual Phase I/II studies of Sotorasib and Tarloxotinib

Adverse events	Tarloxotinib (n=23)		Sotorasib (n=129)	
	Any grade	>G3	Any grade	>G3
QTc prolongation	60.9%	34.8%	-	-
Rash acneiform	43.5%	4.3%	-	-
Diarrhea	21.7%	4.3%	29.5%	2.3%
Nausea	21.7%	0%	20.9%	1.6%
Fatigue	33.3%	0%	23.3%	2.3%

Vomiting	-	-	17.8%	3.9%
Abdominal pain	-	-	17.8%	3.1%
Dyspnea	-	-	16.3%	2.3%
Cough	-	-	15.5%	0%
Back pain	-	-	14.7%	1.6%
Decreased appetite	-	-	14.7%	1%
Headache	-	-	14.0%	0%
AST elevation	-	-	13.2%	2.3%
anemia	-	-	13.2%	4.7%
dizziness	-	-	13.2%	0%
ALT elevation	-	-	11.6%	0%
Constipation	-	-	10.9%	0%
Pyrexia	-	-	10.9%	0%
Insomnia	-	-	10.1%	0%
Myalgia	-	-	10.1%	0%
Peripheral edema	-	-	10.1%	0%
Arthralgia	-	-	10.1%	1.6%

4 SUBJECT SELECTION

4.1 INCLUSION CRITERIA

Patients eligible for study participation must meet all the following criteria:

- 1) Histologically confirmed diagnosis of squamous or non-squamous NSCLC with *KRAS* G12C mutation
- 2) Unresectable or metastatic disease
- 3) No available treatment with curative intent
- 4) Must have previously received treatment with at a platinum-containing chemotherapy regimen. Additional prior therapies for metastatic *KRAS* G12C mutated NSCLC are also permitted.
- 5) Must have previously received at least one month trial of sotorasib or a therapy targeting *KRAS* G12C mutation with documented progression. If sotorasib dose from prior therapy was reduced for toxicity, patients that meet the above criteria are expected to receive study treatment at the reduced dose.
- 6) Must have measurable or evaluable disease as defined by RECIST 1.1
- 7) Age >18 years

- 8) Life expectancy of at least 3 months
- 9) Recovery from adverse effect of prior therapy at the time of enrollment
- 10) Eastern Cooperative Oncology Group (ECOG) performance status of 0 or 1
- 11) Laboratory values within the screening period:
 - a) Absolute neutrophile count > 1000/mm³
 - b) Platelet count > 100,000 /mm³
 - c) Hemoglobin > 8 in the absence of transfusions for at least 2 weeks
 - d) Total bilirubin < 1.5 x upper limit of normal (or < 3 x ULN if associated with liver metastases or Gilbert's disease)
 - e) Aspartate transaminase (AST) or alanine transaminase (ALT) < 3 x ULN (or < 5x ULN if associated with liver metastases)
 - f) Creatinine clearance (CrCl) > 60 mL/min calculated by CKD-EPI or MDRD
- 12) Women of child-bearing potential agrees to use contraception while participating in the study and for a period of 6 months following termination of study treatment
- 13) Completed informed consent process
- 14) Willing to comply with clinical trial instructions and requirements.

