6 TREATMENT/STUDY INTERVENTION

6.1 STUDY TREATMENT AND TREATMENT SCHEDULE

This is a traditional safety and efficacy study of Sotorasib and Tarloxotinib for patients with KRAS G12C mutant NSCLC. Treatment will be administered on an outpatient basis.

Sotorasib will be administered at a recommended Phase 2 dose of 960 mg PO daily.

All patients will receive a weekly tarloxotinib infusion at the RP2Dc determined in the safety lead-in portion of the trial administered as a 1-hour IV infusion on Days 1, 8, 15, and 22 of each 28-day cycle until disease progression or unacceptable toxicity. Radiographic tumor assessment including computed tomography (CT) scans or magnetic resonance imaging (MRI) of chest and abdomen will be performed every 8 weeks (\pm 5 days) from Cycle 1 Day 1, using the same imaging modality per patient.

Tarloxotinib dose calculations do not need to be adjusted within a cycle unless the patient has a $>$ 10% change in body weight. Other dose modifications may be required based on QTc prolongation, infusion-related reactions, and other tarloxotinib-related toxicity. In the safety lead-in portion of the study, an initial 3 patients will be treated at Dose Level 1 based on the body weight measured on Day 1 of each cycle (or within 7 days prior [e.g., Day 22 of the prior cycle]). The dose level for subsequent patient cohorts will be determined using standard 3+3 dose escalation/de-escalation rules using the dose levels indicated in table below.

3x3 design to de-escalate tarloxotinib dosing based on DLTs

Dose level	Sotorasib	Tarloxotinib
-2	960 mg PO daily	75 mg/m ² IV weekly
-1	960 mg PO daily	100 mg/m ² IV weekly
0 (full dose)	960 mg PO daily	150 mg/m ² IV weekly

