11 STATISTICAL CONSIDERATIONS

11.1 STUDY DESIGN

Study CTO # 103048 is a potentially multicenter, non-randomized, single cohort phase IB trial evaluating the safety and efficacy of tarloxotinib in combination with sotorasib in NSCLC patients with KRAS G12C mutation who have progressed on any small molecule KRAS G12C inhibitor.

Safety lead-in

A minimum of 6 patients and as many as 18 patients will be enrolled in a safety lead-in cohort to evaluate the safety of the combination of tarloxotinib and sotorasib. Sotorasib will be held at a fixed dose of 960 mg QD (the approved dose) while the starting dose of tarloxotinib will be the monotherapy RP2D equal to 150mg/m² QW (dose level 1 [DL1]). Following a 3+3 algorithm, an initial 3 patients will be enrolled at DL1. If 0 or 1 of 3 patients experience a DLT, an additional 3 patients will be enrolled to DL1. DL1 will be declared the combination RP2D (RP2D_c) if at most 1 of 6 patients treated at DL1 experience a DLT. Alternatively, if there are 2 or more DLTs observed at DL1, 3 patients will be enrolled at DL -1 and the 3+3 rules repeated for safety evaluation. The RP2D_c will be the highest DL at which at most 1 patient of 6 experiences a DLT. If DL -2 is considered too toxic, additional dose levels below DL -2 to be determined may be considered for safety.

Dose expansion

Once the tarloxotinib RP2D_c is reached, an expansion cohort of up to 12 patients will be enrolled to evaluate the safety of the combination of tarloxotinib and sotorasib. Eligible safety lead-in patients treated at the RP2D_c will be included in the expansion cohort.

The combination of tarloxotinib and sotorasib will not be considered promising if there is weak evidence the true objective response rate (ORR) exceeds 20%. Specifically, the trial will be declared negative if $\text{Prob}(\text{true ORR} > 20\% | \text{observed no. of responses}) < 20\%$, equivalent to observing at most 1 response in 12 patients. We assume the true ORR follows a beta (0.5, 0.5) prior distribution and, conditional on the true ORR, the number of responses follows a binomial distribution. If at least 2 responses in 12 patients are observed, the combination may be considered promising. Given 1 response in 12 patients, the probability the true ORR exceeds 20% is approximately 16%. Given 2 responses in 12 patients, the probability the true ORR exceeds 20% is approximately 42%.

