11.1.2 POPULATIONS FOR ANALYSES

The following analysis sets will be defined for this study.

The **safety analysis set** comprises all enrolled patients who receive any quantity of study treatment, regardless of eligibility. The safety evaluation will be performed based on the first dose of study treatment a patient receives, regardless of the patient's cohort assignment. The safety analysis set will be used for all dosing/exposure and safety analyses.

The **DLT-evaluable population (safety lead-in only)** comprises patients who have either completed the DLT-observation period (1 cycle, 28 days) and received at least 75% of planned doses of the tarloxotinib and sotorasib combination in cycle 1 or have discontinued study treatment or study participation before completing cycle 1 due to a DLT.

The **intention to treat (ITT) analysis set** comprises all patients in the safety analysis set eligible for study inclusion and who meet the inclusion criteria for dose expansion, including eligible safety lead-in patients treated at the RP2D_c. This analysis set will be used for all efficacy analyses.

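### Inclusion 5 and the lead-in dose tables give different sotorasib starting doses for a patient with an earlier toxicity reduction, so an RP2D_c listed with 960 mg may rest partly on lower starting doses

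*Combined protocol and SAP*

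**What the plan says.** **Starting dose.** Criterion 5, in section 4.1 and in the synopsis, requires earlier sotorasib or another KRAS G12C therapy with progression. For those whose sotorasib was cut for toxicity it adds that "patients that meet the above criteria are expected to receive study treatment at the reduced dose". Nothing limits this to the expansion part.

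Section 11.1, repeated in the synopsis, says of the lead-in: "Sotorasib will be held at a fixed dose of 960 mg QD". The tables in sections 1 and 6.1 list 960 mg at all three levels and change only tarloxotinib. The synopsis gives the treatment as "Sotorasib 960 mg PO daily + tarloxotinib IV weekly at the combination RP2D determined in the safety lead-in". Sotorasib 480 mg and 240 mg appear only as on-study reductions (sections 6.5.2 and 7.2.8).

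**Counting.** Under section 11.1 a level becomes the RP2D_c if no more than one of six patients has a DLT. The expansion paragraph opens with "Once the tarloxotinib RP2D_c is reached", and section 6.1 says "All patients will receive a weekly tarloxotinib infusion at the RP2Dc determined in the safety lead-in portion of the trial"; sections 6.5.2 and 7.1.2 use much the same words. Carry-over is stated as "Eligible safety lead-in patients treated at the RP2D_c will be included in the expansion cohort". Section 11.3 adds the DLTs of those lead-in patients to the expansion toxicity count. The DLT-evaluable set in 11.1.2 needs patients who completed cycle 1 to have "received at least 75% of planned doses of the tarloxotinib and sotorasib combination in cycle 1".

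**The concern.** The RP2D of the combination is part of the first primary objective. Criterion 5 foresees patients with an earlier sotorasib reduction, and every entrant has had a KRAS G12C therapy, so such a patient may well reach the lead-in. One part of the plan then points to the patient's own reduced dose and another to 960 mg, with no cross-reference between them.

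If the reduced dose is given and the patient is counted by tarloxotinib level, the level is tabulated with 960 mg but judged partly on someone who did not start there. Each such patient is 1/6 (17%) of the decision set for that level. If the level is declared, the patient is also 1/12 (8%) of the response rule and enters the DLT-E monitoring count. The declared RP2D_c would then carry a sotorasib dose that not all of its supporting patients started.

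**Working it through.** **1. The passages side by side.**

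| Question | Text | Reading |
|---|---|---|
| Starting sotorasib dose after an earlier reduction | Criterion 5: the reduced dose. Sections 11.1, 6.1 and 1: 960 mg at every level | Conflict; no lead-in exemption |
| What defines the dose level and RP2D_c? | Sections 6.1, 6.5.2, 7.1.2 and 11.1 attach the term mainly to tarloxotinib | The patient probably counts at the tarloxotinib level received |
| Is the patient DLT-evaluable? | 11.1.2: 75% of planned doses. Sections 7.1.5, 7.1.6 and 7.2.7 use dose for an administration; 11.2.1.4 allows for protocol-defined adjustments | Probably yes, judged against the patient's own assigned doses |
| Does the first-dose sentence in 11.1.2 settle it? | "The safety evaluation will be performed based on the first dose of study treatment a patient receives" | No; it governs the safety set, not the 3+3 count |

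**2. The plan's own figures.** Section 11.1.1 tabulates the chance of at least one DLT in six as 1 - (1 - p)^6. At p = 0.05, 0.10, 0.20 and 0.30 this gives 0.265, 0.469, 0.738 and 0.882, against 0.26, 0.47, 0.74 and 0.88 in the table. They reproduce. The calculation treats the six as having one common rate.

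**3. How often could this arise?** Let s be the share of entrants with an earlier sotorasib reduction. The documents do not give s; 5% to 30% is an assumed range. Entrants previously treated with a different KRAS G12C agent have no sotorasib dose to carry over, which lowers s. The chance of at least one such patient among six is 1 - (1 - s)^6: 26%, 47%, 74% and 88% at s = 5%, 10%, 20% and 30%. The formula is the same as in step 2, hence the same numbers.

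**4. What could it do to the 3+3 decision?** Let a be the DLT rate for a 960 mg start and b the rate for a reduced start, with k of the six on a reduced start. A level passes with at most one DLT in six.

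- k = 0: (1 - a)^6 + 6a(1 - a)^5
- k = 1: (1 - b)[(1 - a)^5 + 5a(1 - a)^4] + b(1 - a)^5
- k = 2: (1 - b)^2[(1 - a)^4 + 4a(1 - a)^3] + 2b(1 - b)(1 - a)^4

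The documents give no DLT rate by sotorasib dose. As an illustration take b = a ± 0.047. The 4.7% is the largest severe-grade sotorasib entry in section 3.1.7 (anemia). It is not a contrast between doses, is not restricted to cycle 1 or to related events, and is not an upper limit. Both signs are shown because the direction is unknown.

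| a | k = 0 | k = 1 (b lower / higher) | k = 2 (b lower / higher) |
|---|---|---|---|
| 0.10 | 0.886 | 0.901 / 0.870 | 0.916 / 0.854 |
| 0.20 | 0.655 | 0.675 / 0.636 | 0.694 / 0.617 |
| 0.30 | 0.420 | 0.437 / 0.403 | 0.454 / 0.387 |

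For k = 1 the shift is exactly 0.047 × 5a(1 - a)^4. At a = 0.20 that is 0.047 × 0.4096 = 0.019. The shift is about 2 points for one patient and 3-4 points for two. If a = b it is zero.

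**The case against.** Criterion 5 is a specific rule for a named subgroup and the 960 mg statements are general. On a specific-over-general reading a site can dose these patients, and holding sotorasib fixed may mean only that it is not the drug being stepped. A reader might infer that sites have no workable instruction. That goes too far: a workable reading exists, but the plan does not state it, and the dose tables contradict it on their face.

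A reader might also infer that nothing indicates how these patients count. The documents do not support that either. Level and RP2D_c are tied mainly to the tarloxotinib dose, and the synopsis wording can be read as a tarloxotinib dose for use in combination with separately stated sotorasib. Planned doses most naturally means the patient's own. This part of the objection stands: the counting rule is largely inferable. But the same inference places reduced-dose starters inside a level tabulated with 960 mg.

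Criterion 5 gives no mg figure, which is not a defect, since it refers to each patient's own previous dose.

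On size, section 7.2.4 reports similar steady-state exposure from 180 to 960 mg, a range that contains 480 and 240 mg, and section 3.1.6 expects generally non-overlapping toxicity, gastrointestinal events excepted. Sections 11.1.1 and 11.3 let the RP2D_c rest on the totality of data and be revised. Sections 11.2.1.2, 11.2.1.4 and 11.2.4 already summarize prior therapies, dose reductions and intensity, and DLTs. These points limit the consequence. They do not remove the conflict, and none of those summaries is by starting sotorasib dose.

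**Conclusion.** The conflict in starting dose is real for a lead-in patient with an earlier sotorasib reduction. Under the more natural reading of the counting text, such patients enter the 3+3 decision and carry into expansion, so an RP2D_c listed with 960 mg may rest partly on lower starting doses. Severity is minor.

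The size is unknown and may be nil. The shifts of about 2 and 3-4 points rest on the assumed 4.7-point contrast, and the frequencies rest on assumed shares.

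Two stronger conclusions are tempting. One is that the RP2D_c decision would be materially distorted. With assumed DLT rates of 33% at 960 mg and 20% at a reduced start, the pass probability goes from 0.358 to 0.401 with one such patient and 0.448 with two, but neither rate comes from the documents. The other is that the efficacy conclusion could flip. With one response, the posterior probability that ORR exceeds 20% is 0.155 in 12 patients, 0.188 in 11 and 0.226 in 10. Crossing the 20% cut-off requires two non-responders to be left out and not replaced, which the plan nowhere says. Efficacy-set membership of eligible patients enrolled directly into expansion is not in doubt.

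**What to change.** Reconcile criterion 5 (section 4.1 and synopsis) with the lead-in text and tables (synopsis, sections 1, 6.1 and 11.1). Which dose rule applies is for the sponsor to decide.

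Then make the 3+3 count and the treated-at-the-RP2D_c wording in 11.1 and 11.1.2 agree with that choice, so that 11.3 follows. If reduced-dose starters count, report the declared RP2D_c with the sotorasib starting doses it rests on, and list DLTs and DLT-Es by starting sotorasib dose. If they do not count, say whether they are replaced.

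The cost is a few sentences and one listing, or possibly replacing a lead-in patient if the sponsor decides that such patients do not count.
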